#### CONFIDENTIAL AND PROPRIETARY

Study Protocol	>∕ smith&nephew
A prospective, multi-center, single arm PMCF study to evaluate the safety and performance of ENTACT™ (Next Generation) resorbable septal staple system for septoplasty	Number: ENTACT.ENT.PRO.SEP.2019.05
	Version: 2.0, 27Aug2020
	Page: Page 31 of 94

Indications	The ENTACT Septal Stapler delivers implantable septal staples which are intended to connect internal tissues to aid healing and for approximation of soft tissues during nasal septal surgery	None
Surgical Technique/ Deployment Methods	1. If there is no cartilage between the mucoperichondrial flaps, the staples can be delivered unilaterally. If cartilage is present, stapling the flaps bilaterally may be considered.	None
	2. Remove protective silicone cover from the distal end of the stapler.	
	3. Unfold and gradually remove pull tab from the distal end of the stapler.	
	4. Insert the distal tip of the ENTACT Septal Stapler in the nose, one arm in each nostril.	
	5. Plan placement of staples, so they are spaced approximately 15 mm apart or as deemed necessary from each other.	
	6. Place the stapler against the mucoperichondrial flap, keeping stapler as perpendicular to the tissue surface as possible and depress handle until an audible click is heard to deploy each staple.	
	7. Release handle until a second audible click is heard before repositioning the distal tip of the stapler.	
	8. If necessary, repeat this procedure in the opposite cavity.	
	9. Visually inspect both nasal cavities to assure adequate approximation and sufficient penetration of the staples.	
	10. The device is empty when the blue indicator within the clear implant housing is against the distal tip. Firing an empty device will cause the implant guide needle to pierce and make a hole in the septum without placement of an implant.	
	staples.	

Study Protocol	% smith&nephew
A prospective, multi-center, single arm PMCF study to evaluate the safety and performance of ENTACT ™ (Next Generation) resorbable septal staple system for septoplasty	Number: ENTACT.ENT.PRO.SEP.2019.05
	Version: 2.0, 27Aug2020
	Page: Page 32 of 94

The Next Generation Smith+Nephew ENTACT Septal Stapler described in **Table 6.1.3-1** can be considered comparable to the Previous Generation of the ENTACT Septal Stapler for the following reasons:

- Clinical

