# 6.5 **SURGICAL TECHNIQUE**

All study-related procedures with the ENTACT Septal Stapler must be performed according to the recommended surgical technique described in the protocol or in a separate instructional document and product labeling (e.g., IFU) as applicable.

Surgeons selected to participate in this study will be familiar with using the ENTACT Septal Staples system.

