# 7.2 INCLUSION CRITERIA

The patient will be eligible for the study if he or she meets all of the following inclusion criteria at the baseline screening:

This document contains information that is confidential and proprietary to Smith + Nephew PLC and Smith + Nephew, Inc. and is intended for use only by Smith + Nephew and its manufacturer. It shall not be reproduced or copied in whole or in part, nor shall the contents be disclosed by any means without prior written permission from Smith + Nephew, nor shall anyone make any use of it that is contrary to the expressed or implied wishes of Smith + Nephew.
Study Protocol	% smith&nephew	
A prospective, multi-center, single arm PMCF study to evaluate the safety and performance of ENTACT™ (Next Generation) resorbable septal staple system for septoplasty	Number: ENTACT.ENT.PRO.SEP.2019.05	
	Version: 2.0, 27Aug2020	
	Page: Page 37 of 94	

- 1. Able and willing to give informed consent by voluntarily providing written informed consent in accordance with governing Institutional Review Board (IRB);
- 2. Clinically significant deviation of the nasal septum;
- 3. Willing and able to make all required study visits;
- 4. Able to read and understand the approved informed consent form and patient reported outcome assessments (written and oral).

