#### 8.4.3 Investigator Training

Prior to the clinical trial, the clinical research associate (CRA), coordinating with the persons in charge of the study sites, will train the Investigators on the study protocol, making sure they are familiar with the use of investigational medical device, and implement subject enrollment strictly in accordance with the inclusion criteria and exclusion criteria, conduct relevant examinations according to the protocol requirements, also master all new device-related information found during the clinical trial, thus to minimize the interferential factors. The follow-up exams will be delegated to Investigators not involved in the procedure to reduce potential bias by the surgeon.

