## 9. STUDY PROCEDURES

### 9.1 VISITS AND EXAMINATIONS

None of the listed activities are undertaken by Sponsor personnel.

Schedule of Events	Patient screening and		Post-operative patient visits		
	surgery				
	Screening/Pre- Operative ≤ 30 days	Surgery Day 0	FU time point Day 5±2	FU time point Day 21±7	FU time point Day 42±7
Informed Consent	Х	-	-	-	-
Inclusion/Exclusion	Х	-	-	-	-
Demographics: Medical History	Х	-	-	-	-
Operative data (Intra- operative delivery success, intra- operative time to deploy staples to complete septoplasty)	-	х	-	-	-
Discharge data	-	Х	-	-	-
Visual assessment of nasal cavity	-	-	Х	Х	х
NOSE score	Х	-	Х	Х	Х
Visual Analog Scale	Х	-	Х	Х	Х
Concomitant Medications, Procedures	Х	х	х	х	х
Safety assessment (AE/SAE/ADE/DD)	-	Х	Х	Х	X

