### ----- Do not proceed until consent has been obtained -----

- 2. Obtain demographic information and medical history, including information on all concomitant medications/therapies.
- 3. Screen the subject for protocol inclusion/exclusion criteria.
- 4. Assign the subject a Subject ID.
- 5. Complete Screening and Enrollment Log.
- 6. Complete NOSE score assessment and VAS pain score.

This document contains information that is confidential and proprietary to Smith + Nephew PLC and Smith + Nephew, Inc. and is intended for use only by Smith + Nephew and its manufacturer. It shall not be reproduced or copied in whole or in part, nor shall the contents be disclosed by any means without prior written permission from Smith + Nephew, nor shall anyone make any use of it that is contrary to the expressed or implied wishes of Smith + Nephew.

Study Protocol	% smith&nephew
A prospective, multi-center, single arm PMCF study to evaluate	Number:
the safety and performance of ENTACT™ (Next Generation) resorbable septal staple system for septoplasty	ENTACT.ENT.PRO.SEP.2019.05
	Version: 2.0, 27Aug2020
	Page: Page 49 of 94

7. Subjects will be instructed to return for the Operation Visit (Procedure) as scheduled by the site.

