## 9.1.2 Treatment/Operation Visit (Visit 2)

- 1. Query subject regarding any changes in general health and the use of concomitant medications.
- 2. Commence treatment/operation.
- 3. Confirm eligibility criteria
- 4. If any adverse device effects or device deficiencies are observed or reported, they must be recorded as instructed in **Section 12**, adverse events and device deficiencies. Also record concomitant medications/therapies used to treat AEs.
- 5. Record Intra-operative delivery success, total operation time and Intra-operative time for operative closure with ENTACT septal stapler.
- 6. Record device identification information for the stapler (e.g., Unique Device Identifier, Lot Number, Serial Number, Catalogue Number) and the number of staples used.
- 7. Instruct the subject on proper postoperative care/procedures, including any contraindicated treatments/medication(s).
- Instruct the subject on follow-up procedures, including returning the treatment facility in 5 days (± 2) days for follow-up visit.
- 9. Complete Operation and Discharge Visit CRFs.
- 10 If applicable, complete an End of Study CRF.

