### 10.4 EFFICACY ANALYSIS

## **10.4.1 Analysis of Primary Endpoint**

Data will be collected on whether the septum wall appearance and need for re-intervention at the surgery site are due to the device or the procedure. Only those that are device-related will contribute to the primary endpoint analyses, in line with the primary objective of this study. A binary variable will be defined as follows; one if all five of the following criteria are true and 0 if at least one of the criteria is false:

- Septum wall straight appearance
- Complete coaptation of perichondrial flaps on septum wall
- Absence of significant local tissue reaction at the staple site
- Absence of hematoma swelling at the staple site
- No need for re-intervention at the surgery site

Clinical success will be inferred for a patient if their binary variable is 1. Clinical success will be reported as a count and percentage with a 95% CI using Clopper-Pearson Exact methodology. A logistic model will be used to evaluate the adjusted and unadjusted models for the primary outcome variable. The variables considered important and to be included in the final model are age and BMI. All other baseline and medical factors collected at baseline will be evaluated for

This document contains information that is confidential and proprietary to Smith + Nephew PLC and Smith + Nephew, Inc. and is intended for use only by Smith + Nephew and its manufacturer. It shall not be reproduced or copied in whole or in part, nor shall the contents be disclosed by any means without prior written permission from Smith + Nephew, nor shall anyone make any use of it that is contrary to the expressed or implied wishes of Smith + Nephew.

Study Protocol	Smith&nephew
A prospective, multi-center, single arm PMCF study to evaluate the safety and performance of ENTACT ™ (Next Generation) resorbable septal staple system for septoplasty	Number: ENTACT.ENT.PRO.SEP.2019.05
	Version: 2.0, 27Aug2020
	Page: Page 56 of 94

importance in adjusted models and only those statistically significant in an unadjusted model will be considered in the final model.

This analysis will be carried out using the FAS as the primary analysis population and the PP population using for sensitivity analysis.

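### Only a device-related crooked septum counts in the primary endpoint, but no end-of-surgery septal finding is listed to support that attribution when Day 5 is already crooked or missing

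*Combined protocol and SAP*

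**What the plan says.** **Schedule.** In protocol Table 9.1.1-1 the row "Visual assessment of nasal cavity" has dashes at Screening and Surgery and marks at Days 5, 21 and 42. Section 8.3.2 has the same five yes/no items examined at Day 5 as at Day 21.

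**Before surgery.** Inclusion criterion 2 in Section 7.2 is "Clinically significant deviation of the nasal septum". The outcome step at Visit 1 (Section 9.1.1) is "Complete NOSE score assessment and VAS pain score". No grade or description of the septum is listed.

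**At surgery.** Section 9.1.2 says "Record Intra-operative delivery success, total operation time and Intra-operative time for operative closure with ENTACT septal stapler", and adds device identifiers and the number of staples. Step 9 of the surgical technique in Table 6.1.3-1 tells the operator: "Visually inspect both nasal cavities to assure adequate approximation and sufficient penetration of the staples". Section 6.5 makes the technique binding: procedures "must be performed according to the recommended surgical technique described in the protocol", or in separate instructions and labeling.

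**Follow-up examiner.** Section 8.4.3: "The follow-up exams will be delegated to Investigators not involved in the procedure".

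**Primary analysis.** Section 10.4.1 collects data on "whether the septum wall appearance and need for re-intervention at the surgery site are due to the device or the procedure" and admits only the device-related ones to the primary endpoint analysis. It gives no rule for the attribution and does not say who makes it. Section 8.3.1, by contrast, treats any NO among the five items as a failure.

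**The concern.** By Section 4.1, a septum is straightened by the surgeon's resection or reshaping of cartilage and bone. By Section 6.1.1, the staples hold the tissues together while they heal. A NO for straightness at Day 21 can therefore arise in two ways: the septum was never fully corrected, or the correction was achieved and then lost. Section 10.4.1 needs this distinction, because a finding put down to the procedure does not contribute to the primary endpoint.

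The fact that bears most directly on it is the state of the septum when the operation ended. That is not among the listed data, and the follow-up examiner did not see it. It cannot be recovered reliably afterwards. With few failures expected, one or two doubtful attributions would visibly move the reported success rate.

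**Working it through.** **1. What Day 5 can and cannot settle.** Take a septum scored not straight at Day 21:

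| Day 5 finding | What the listed data show |
|---|---|
| Straight | It had been corrected, so never straightened is ruled out. A device cause is still not proved. |
| Not straight | Either never corrected, or corrected and lost before the visit. Cannot be separated. |
| Missing | Same two possibilities. Cannot be separated. |

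The second row matters for this device. The notes to Table 9.1.1-1 describe the Day 5 visit (window ±2 days) as the one that covers fixation during initial healing. A loss in those days, when the staple is doing its work, would already be present at the visit. The third row can occur in the primary population, because the FAS in Section 10.2 needs only one post-baseline visit.

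**2. Whether another listed item fills the gap.** Delivery success appears in Section 10.4.2 as successful staple deployment, which is not an anatomical result. Step 9 of the technique covers approximation and staple penetration, not straightness, and is not listed for recording. The eligibility check shows only that every subject starts with a deviation.

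**3. Size.** The plan gives no figure for this point, so the following is an illustration.

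Inputs: 36 evaluable subjects, 10% dropout and an assumed 92% success rate (Section 11); Clopper-Pearson 95% interval (Section 10.4.1). The plan's own numbers reproduce:
- 36/(1 − 0.10) = 40.
- With a Wald interval at 92%, n = 36 gives an 84.3% probability of a half-width within 11 points, against the stated minimum of 80%.

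Assumption: three septa crooked at Day 21, all in the unresolved rows, and no other failure. Three is close to 36 × 0.08 = 2.9, but the 92% refers to tissue fixation at one week, not to this composite, so the count is only a scale.

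Formula for x successes in n: lower limit = the 0.025 quantile of Beta(x, n − x + 1); upper limit = the 0.975 quantile of Beta(x + 1, n − x). When x = n, the lower limit is 0.025^(1/n).

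| Called device-related | Success (others scored as success) | 95% CI |
|---|---|---|
| 3 | 33/36 = 91.7% | 77.5 to 98.3 |
| 2 | 34/36 = 94.4% | 81.3 to 99.3 |
| 1 | 35/36 = 97.2% | 85.5 to 99.9 |
| 0 | 36/36 = 100% | 90.3 to 100 |

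Each attribution moves the estimate by 1/36 = 2.8 points. Over the three cases the estimate moves 8.3 points and the lower limit 0.9026 − 0.7753 = 0.127, or 12.7 points.

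Section 10.4.1 does not say whether a procedure-related NO is scored as success or leaves the denominator. If all three were removed, the result would be 33/33 with lower limit 0.025^(1/33) = 0.894.

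Range: with no crooked septa, attribution changes nothing. With four, the contrast is 32/36 = 88.9% (73.9 to 96.9) against 36/36.

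**The case against.** The strongest reply is that the study already has the reference it needs. Day 5 records the same five items, screening confirms a deviation, and the operator must inspect both cavities after stapling. Operation and Discharge CRFs are also completed (Section 9.1.2), and their fields are not shown. The Visit 2 list is not exhaustive: Section 10.4.2 reports stapler misfires, which that list does not itemise. Nothing denies the attributor the operative notes.

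Much of this stands, and it rules out several stronger readings that a reader might infer:

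- *That nobody assesses the septum or flaps before surgery or at its end.* The eligibility check and step 9 contradict this. What is missing is a listed record of the end state, above all for straightness.
- *That a crooked septum at Day 21 can never be classified.* Where Day 5 was straight, never straightened is excluded.
- *That the absent examiner must make the attribution.* Section 10.4.1 names no one. If the operating surgeon makes it, the bias that Section 8.4.3 is meant to reduce returns. A record made at the time helps in either case.
- *That coaptation is split in the same way.* Section 10.4.1 applies the split only to septum appearance and re-intervention.
- *That later loss of straightness should be counted against the device by default.* The staples hold the flaps, so a change after Day 5 does not establish a device cause.

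The reply does not reach the septum already crooked, or not examined, at Day 5. The operative CRFs may hold the item, but the protocol does not require it.

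**Conclusion.** The point holds in a limited form. For a septum crooked at Day 21 and either crooked or unexamined at Day 5, the listed study data do not show whether it was ever straight. Section 10.4.1 nevertheless makes the primary result depend on a device-or-procedure attribution, without a rule or a named attributor.

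The size depends on how many subjects fall in that group, which the documents do not allow one to predict. With three among 36 and no other failures, the reported success lies anywhere from 91.7% to 100%, and the lower limit from 77.5% to 90.3%. The upper ends assume that a procedure-related NO is scored as success. This does not show that the attribution will be wrong or will favour the device, only that it lacks its most direct evidence. The matter is worth correcting because the correction is cheap and the missing observation cannot be reliably recovered later.

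**What to change.** 1. **Operation CRF (Section 9.1.2).** At the inspection in step 9 of the technique, record two items: septum straight (yes/no) and flaps coapted (yes/no).
2. **Section 10.4.1.** Require the attribution of a crooked septum to use this record together with the Day 5 finding. Make it only after the Day 21 yes/no items have been entered, and name who makes it. State whether a procedure-related NO is scored as success or leaves the denominator.
3. **Second presentation of the primary endpoint.** Also report it with every NO counted as failure whatever its attribution, as Section 8.3.1 reads. The surgeon's entry then does not alone decide the result.

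Side and site of the deviation at Screening could be added, but would contribute little, since every eligible subject starts deviated.

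**Cost.** Two CRF fields, a short rule and one further line in the primary results table, with no new visit or assessor. Step 9 does not now cover straightness, so the operator is asked to note one more thing during a look already taken. The real downside is that the operating surgeon makes the entry. An optimistic entry pushes a later NO towards the device, and an entry of not straight pushes it towards the procedure, so the bias can run either way. Item 3 limits that. The record improves the attribution but does not by itself prove cause.

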### Table 9.1.1-1: Study Procedures by Visit

#### CONFIDENTIAL AND PROPRIETARY

This document contains information that is confidential and proprietary to Smith + Nephew PLC and Smith + Nephew, Inc. and is intended for use only by Smith + Nephew and its manufacturer. It shall not be reproduced or copied in whole or in part, nor shall the contents be disclosed by any means without prior written permission from Smith + Nephew, nor shall anyone make any use of it that is contrary to the expressed or implied wishes of Smith + Nephew.

Study Protocol	Smith&nephew
A prospective, multi-center, single arm PMCF study to evaluate the safety and performance of ENTACT™ (Next Generation) resorbable septal staple system for septoplasty	Number: ENTACT.ENT.PRO.SEP.2019.05
	Version: 2.0, 27Aug2020 Page: Page 48 of 94

End of Study/Subject		*	*	*	×.
disposition	-				X

\*As needed

Post-operative visits:

- (1) Day 5±2 covers the true "fixation" period for initial healing
- (2) Day 21±7 covers the standard of care for patient follow-up

(3) Day 42±7 covers the clinical follow-up duration associated with the lifetime of the device Notes:

Subjects who have undergone a re-intervention procedure of the implant will be considered terminated from the study from the date of the re-intervention. Study related data will not be collected following the date of the re-intervention.

All concomitant medications/ procedures including any associated with an AE, SAE or SADE will be recorded.

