# **STUDY SCHEDULE**

Visit Type/name	Frequency / Time point
Screening/Pre-Operative (Visit 1)	(≤ 30 days) Within 30 days of Visit 2
Operative (Visit 2)	Day 0 - Surgery
Follow-up (Visit 3)	Day 5±2
Follow-up (Visit 4)	Day 21±7
End of Study (Visit 5)	Day 42±7

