### 8.3 **STUDY ENDPOINTS**

#### 8.3.1 Primary Endpoint

At the 21-day follow-up visit, the clinician will examine the patient's nasal cavity and will confirm:

- Septum wall straight appearance (yes/no);
- Complete coaptation of perichondrial flaps on septum wall (yes/no);
- Absence of significant local tissue reaction at the staple site (yes/no);
- Absence of hematoma swelling at the staple site (yes/no);
- No need for re-intervention at the surgery site (yes/no);

If all the answers to the questions above are "YES" then clinical success will be inferred (if any answer is "NO" then repair failure will be inferred).

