## 10.2 ANALYSIS POPULATIONS

The following analysis populations will be used for this study:

- Safety population (SAF): This includes all patients who have received the study device.
- Full Analysis Set (FAS): This includes all patients who were recruited into the study and have at least one post-baseline visit.
- Per-Protocol (PP) population: This includes all subjects in the FAS who have no significant protocol deviations and who meet all the inclusion/exclusion criteria.

Statistical analysis will be performed using each of the patient populations as follows: Analysis of the primary and secondary endpoints will be performed separately using both the FAS and PP populations. All safety analyses will utilize the SAF population.

This document contains information that is confidential and proprietary to Smith + Nephew PLC and Smith + Nephew, Inc. and is intended for use only by Smith + Nephew and its manufacturer. It shall not be reproduced or copied in whole or in part, nor shall the contents be disclosed by any means without prior written permission from Smith + Nephew, nor shall anyone make any use of it that is contrary to the expressed or implied wishes of Smith + Nephew.

Study Protocol	> ∕ smith&nephew
A prospective, multi-center, single arm PMCF study to evaluate the safety and performance of ENTACT™ (Next Generation) resorbable septal staple system for septoplasty	Number: ENTACT.ENT.PRO.SEP.2019.05
	Version: 2.0, 27Aug2020
	Page: Page 55 of 94

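### A device-related re-intervention before the first follow-up visit can fall outside the primary denominator, and one between Day 5 and Day 21 has only an implied primary value

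*Combined protocol and SAP*

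**What the plan says.** - **End of participation (notes to Table 9.1.1-1).** "Subjects who have undergone a re-intervention procedure of the implant will be considered terminated from the study from the date of the re-intervention". The next sentence adds: "Study related data will not be collected following the date of the re-intervention". Section 7.9.1 also lists re-intervention among the reasons for which the investigator may withdraw a subject.
- **Endpoint timing (8.3.1).** "At the 21-day follow-up visit, the clinician will examine" the nasal cavity and answer five yes/no items, one of which is that no re-intervention is needed at the surgery site. Any negative answer means failure.
- **Primary variable (10.4.1).** It is "one if all five of the following criteria are true and 0 if at least one of the criteria is false". For septum appearance and re-intervention, attribution to device or procedure is recorded: "Only those that are device-related will contribute to the primary endpoint analyses".
- **Primary population (10.4.1, 10.2).** "This analysis will be carried out using the FAS as the primary analysis population". The FAS is defined as follows: "This includes all patients who were recruited into the study and have at least one post-baseline visit".
- **Enrolment (7.6).** A subject counts as enrolled once consent is complete and the study product has been used.
- **Missing data.** Sections 8.3.6 and 11 treat attrition as a sample-size matter (36 raised to 40). Section 10 defers further detail to a SAP due before database lock. No section gives a rule for a missing Day-21 value.

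**The concern.** The event that ends follow-up is itself one of the five ways to fail the primary endpoint. Losing such a subject is therefore not ordinary drop-out. It removes a known failure and can only push the success rate up. Raising enrolment from 36 to 40 protects precision but does nothing about this bias. The primary result is a single proportion from about 36 to 40 subjects, so one subject visibly moves the estimate and its interval.

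**Working it through.** **Step 1: the plan's own figure.** Inputs from Section 11: success rate 0.92, two-sided 95% interval, precision ±0.11, 36 evaluable subjects, 10% drop-out. With the normal-approximation interval, the half-width is 1.96 × √(p̂(1 − p̂)/n). At n = 36, 32 successes give 0.103 (meets 0.11) and 31 give 0.113 (does not). The probability of at least 32 successes at 0.92 is 84.3%, which agrees with the stated minimum of 80%. The same formula gives 78.4% at n = 30 and 90.3% at n = 40, the two ends of the range quoted in Section 11. Enrolment: 36/(1 − 0.10) = 40. This point leaves the sample size unchanged.

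**Step 2: when the device-related re-intervention occurs.**

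| Time of re-intervention | In the FAS? | Primary value |
|---|---|---|
| Before the Day-5 visit | Only if surgery counts as a post-baseline visit | 0 implied by 10.4.1 if in the FAS; otherwise not counted |
| Between the Day-5 and Day-21 visits | Yes | 0 implied by 10.4.1; no Day-21 examination as 8.3.1 describes |
| Need found at the Day-21 visit | Yes | 0, stated |

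On the first row, the Study Schedule and Section 9.1.2 number the operation as Visit 2, while the schedule of events in Section 9.1 groups it with screening, apart from the post-operative visits. Section 7.6 makes treatment part of enrolment, and Section 7.7 classes consented subjects who are never enrolled as screen failures. If surgery counted as the required visit, the condition would therefore exclude almost nobody. The more natural reading is that a follow-up visit is meant.

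**Step 3: size.** With s successes and n subjects including k early re-interventions, omitting those k changes the rate by s/(n − k) − s/n = sk/[n(n − k)]. Intervals are Clopper-Pearson 95%, as Section 10.4.1 plans.

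| Case | Omitted | Counted as failure | Shift |
|---|---|---|---|
| n = 40, s = 36, k = 1 | 36/39 = 92.3% (79.1 to 98.4) | 36/40 = 90.0% (76.3 to 97.2) | 36/(40 × 39) = 2.3 points |
| n = 37, s = 33, k = 1 | 33/36 = 91.7% (77.5 to 98.2) | 33/37 = 89.2% (74.6 to 97.0) | 33/(37 × 36) = 2.5 points |
| n = 40, s = 36, k = 2 | 36/38 = 94.7% (82.3 to 99.4) | 36/40 = 90.0% (76.3 to 97.2) | 72/(40 × 38) = 4.7 points |
| n = 38, s = 33, k = 2 | 33/36 = 91.7% (77.5 to 98.2) | 33/38 = 86.8% (71.9 to 95.6) | 66/(38 × 36) = 4.8 points |

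The rows with s = 33 keep the planned 36 evaluable subjects, with 33 successes because 33/36 is the nearest attainable rate to 92%. The values of k are assumptions; k = 0 gives no bias.

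**The case against.** **Post-baseline is not post-operative.** Eligibility is judged at a baseline screening (7.2, 7.3), change scores run from the pre-operative visit (10.4.2), and surgery is one of five visits (7.1). On that wording every treated subject is already in the FAS. This is a fair reading and the reason the exclusion cannot be called certain. It leaves the condition almost without effect, however, and the text does not settle the matter.

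**The failure value is already there.** A reader might infer that a re-intervention between Day 5 and Day 21 has no primary value, or that the plan directs such subjects to be set to missing. The documents support neither. Section 10.4.1 gives 0 when any criterion is false, and the sentence carries no visit condition. Data stop only after the date of the re-intervention, so the event itself is on record. What remains is that Section 8.3.1 ties the items to an examination that will not take place, and nothing says the value applies without it.

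**The SAP may cover it.** It may; the separate SAP announced in Section 10 is not among the documents reviewed. But it is due only before database lock in an unblinded single-arm study (8.2), so a rule left until then could be chosen with outcomes known.

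**Scope.** Mandatory termination covers re-intervention of the implant, which is narrower than re-intervention at the surgery site in 8.3.1. This stands: the point should not be extended to every re-intervention.

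**Size.** The shift is small beside ±11 points, and Section 10.4.1 sets no pass mark, so no stated decision reverses. Both are correct. A reader might also take the one reoperation among 101 subjects in Section 4.2.2 as an expected frequency. Its timing is not given and it concerns an earlier device generation, so no frequency is derived here.

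**Conclusion.** The point holds in a limited form. A device-related re-intervention of the implant before the first follow-up visit can be left out of the primary denominator although it is a primary failure. This rests on reading the FAS condition as a follow-up visit, which the text favours but does not state. For one between the Day-5 and Day-21 visits, failure is implied and should be made explicit. Any omission biases the success rate upward, by about 2.3 to 2.5 points for one subject and 4.7 to 4.8 for two, under the assumed counts shown. The actual number may be zero. A reader might infer that such failures would be concealed. They would not: device-related re-intervention is a safety endpoint (8.3.3), summarized in the safety population (10.5). What is at risk is the primary estimate. The point should be fixed because the bias has one direction and is easily avoided.

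**What to change.** - **Section 10.2:** define the FAS as all consented subjects treated with the study stapler, and remove the post-baseline-visit condition. This set nearly coincides with the safety population, which is acceptable in a single-arm study.
- **Section 10.4.1:** state that the primary variable is 0 for any device-related re-intervention on or before the Day-21 visit, whether or not a Day-21 examination exists.
- **Data after re-intervention:** reconcile the notes to Table 9.1.1-1 and Section 8.3.3, which stop collection at re-intervention, with Section 9.1.7 (an end-of-study visit where possible) and Section 12.5.1 (continued follow-up of related events). These can coexist, but the text should say which data are kept.
- **Left to the SAP:** the handling of procedure-related re-interventions and of other missing Day-21 examinations.

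The cost is wording only, with no added subjects, visits or procedures. The downside is that the reported success rate may be lower, by about 2.3 to 2.5 points for one failure that would otherwise be omitted.
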